#### 13.2.2. True negative patient:

13.2.2.1. **Ga PSMA-HBED-CC PET/CT negative for regional nodes by internal blind reader;** pathology at prostatectomy negative for regional nodes as defined in Section 12.2.1.2 .

#### 13.2.3. False positive patient:

13.2.3.1. **Ga PSMA-HBED-CC PET/CT positive for regional nodes**

**by internal blind reader**, pathology at prostatectomy is negative, and imaging after prostatectomy demonstrates that node is no longer present as defined in Section 12.2.1.2.

13.2.3.2.  **$^{68}\text{Ga}$  PSMA-HBED-CC PET/CT positive for regional node by internal blind reader**, but pathology at prostatectomy is positive for node but in a different nodal region than the node seen on PSMA PET.

13.2.4. False negative patient:

13.2.4.1.  **$^{68}\text{Ga}$  PSMA-HBED-CC PET/CT negative for regional nodes by internal blind reader**, but pathology at prostatectomy is positive for regional nodes.

13.2.5. Non-evaluable patient:

13.2.5.1. Any subject that does not have sufficient data to meet the criteria for definition of true positive patient, true negative patient, false positive patient, or false negative will be classified as non-evaluable.

13.2.5.2. Patients with extrapelvic nodal metastases will not be included in this analysis for the primary endpoint if patients do not undergo prostatectomy.

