## 12.2. Reference standard definition:

12.2.1. Histopathology/Biopsy will be the primary determinate of tissue positivity and negativity for prostate cancer disease. Pathology date, organ, and location as well as any notes related to the pathology will be obtained from the subject chart. The anatomical region/sub-region the pathology occurred in will be assigned by the investigator team:

Ga-PSMA-HBED-CC positive findings are aimed to be confirmed by histopathology/biopsy if clinically feasible. Pathology performed 60 days before or after the Ga-PSMA-HBED-CC PET will be available for correlation.

Histopathological procedures and biopsies will be performed as clinically indicated and as per institutional protocol.

12.2.1.1. Lymph Nodes, Visceral Lesions, and Bone Lesions positive for disease by pathology.

- Lesions with positive pathologic confirmation will be regarded as positive for disease. The regionality of the resected tissue will be assigned into respective regions and sub-regions as described above in Table 12.2.

12.2.1.2. Lymph Nodes and Visceral Lesions negative for disease by pathology.

- Tissue removed and negative for pathology are considered negative for prostate cancer disease, unless subsequent conventional imaging or Ga-PSMA-HBED-CC PET imaging demonstrates that targeted tissue were not resected. In this case:

- i. Subjects can be rescanned with dedicated CT, MRI, or Ga-PSMA-HBED-CC PET/CT to determine if the suspicious Ga-PSMA-HBED-CC tissue was removed. If the tissue is confirmed as removed, this is considered negative for disease.

ii. If  $^{68}\text{Ga}$ -PSMA-HBED-CC PET/CT positive tissue is still present, a needle biopsy can be pursued at the discretion of the treating physician. Images of the procedure will be reviewed to determine if the correct tissue was biopsied.

- If the  $^{68}\text{Ga}$ -PSMA-HBED-CC PET/CT positive tissue was biopsied, a negative pathologic finding of the biopsied tissue is considered negative for disease.
- If the  $^{68}\text{Ga}$ -PSMA-HBED-CC PET/CT positive tissue was biopsied, a positive pathologic finding of the biopsied tissue is considered positive for disease.
- If biopsy or re-biopsy is not performed, or the wrong tissue was biopsied, change in node size as measured by conventional imaging and as defined below will be the criteria by which disease status will be defined.

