#### 13.2.1. True positive patient:

13.2.1.1. **Ga PSMA-HBED-CC PET/CT positive for a regional node by internal blind reader:** pathology at prostatectomy is positive for a regional node that correlates in location to the PET images (location on pathology is determined by the urologist at the time of the surgery). Only one node needs to correspond between imaging and pathology for a patient to be considered a true positive.

13.2.1.2. **Ga PSMA-HBED-CC PET/CT positive for regional nodes by internal blind reader,** pathology negative for regional nodes, imaging after prostatectomy demonstrates the same node was not removed at surgery, and follow-up biopsy or imaging demonstrates presence of nodal disease as defined in Section 12.2.1.2 .

13.2.1.3. **Conventional imaging criteria for positive node on follow-up imaging:** imaging within 3-12 months, the node decreases by more than 30% (for patients undergoing systemic treatment or focal therapy at this site) or increase by more than 20% in short axis diameter in the absence of treatment (with a minimum of 3 mm in change in size) as defined in Section 12.2.2.1 .

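### The false-positive rule in 13.2.3.1 reverses the default of Section 12.2.1.2, which it cites; read literally, it can drop PET-positive, pathology-negative patients and raise specificity and PPV

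*Combined protocol and SAP*

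**What the plan says.** Section 12.2.1.2 sets the reference standard for nodes that are negative on pathology: "Tissue removed and negative for pathology are considered negative for prostate cancer disease, unless subsequent conventional imaging" or a repeat PSMA PET shows that the target was not resected. It then gives two branches. Under item i, a rescan can be done: "If the tissue is confirmed as removed, this is considered negative for disease". Under item ii, the tissue is still present and has been correctly biopsied: "a negative pathologic finding of the biopsied tissue is considered negative for disease".

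Section 13.2.3.1 defines an FP patient as PET positive, where "pathology at prostatectomy is negative, and imaging after prostatectomy demonstrates that node is no longer present as defined in Section 12.2.1.2".

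The other per-patient rules that matter here are:
- 13.2.1.2, true positive (TP) after negative pathology: "imaging after prostatectomy demonstrates the same node was not removed at surgery, and follow-up biopsy or imaging demonstrates presence of nodal disease".
- 13.2.1.3, a further TP route headed "Conventional imaging criteria for positive node on follow-up imaging". As printed it has no pathology condition.
- 13.2.2.1, true negative (TN): PET negative and "pathology at prostatectomy negative for regional nodes as defined in Section 12.2.1.2". No imaging condition is stated.
- 13.2.5.1, the residual class: "Any subject that does not have sufficient data to meet the criteria for definition of true positive patient", or any of the other three categories, is non-evaluable.

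**The concern.** In 12.2.1.2, imaging can only overturn a negative pathology result. In 13.2.3.1, imaging is needed before that result counts. This follows item i of the cited section but not its default, so two analysts could classify the same patient differently.

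The extra proof is asked only of PET-positive patients whose pathology is negative, which is the group that lowers specificity and PPV. Both measures are in primary objective 1.1.1. Section 13.1 plans to use the results, possibly combined with those of other sites using the same reference standard definitions, to design a larger study. The classification rule therefore has to be unambiguous.

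**Working it through.** **1. Does any category take the patient?** Take a patient who is PET positive for a pelvic node, has negative regional pathology and has no post-operative imaging.
- 13.2.1.1 (TP) and 13.2.3.2 (FP) need positive pathology: not met.
- 13.2.1.2 and 13.2.1.3 (TP) need imaging: not met.
- 13.2.2.1 (TN) and 13.2.4.1 (FN, false negative) need a negative PET: not met.
- 13.2.3.1 (FP) needs imaging that shows the node gone: not met.

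Only 13.2.5.1 remains. Under 12.2.1.2 the same patient is negative for disease, hence an FP.

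**2. Retained node with a correctly targeted negative biopsy.** 12.2.1.2 ii calls this negative for disease. The node is still present, so 13.2.3.1 is not met. The patient is unassigned unless 13.2.1.3 applies, which would make the patient a TP if the size criteria are met. But 13.2.1.3 rests on 12.2.2.1, and 12.2.2 is meant for cases without pathology, so precedence is unclear.

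**3. Direction.** Let k FP patients be dropped. Specificity goes from TN/(TN+FP) to TN/(TN+FP−k), and PPV from TP/(TP+FP) to TP/(TP+FP−k). Neither can fall. TP/(TP+FN) and TN/(TN+FN) contain no FP and do not change. (Section 13.1 prints sensitivity with TP+FP as denominator. That expression is PPV and would move with it.)

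**4. Size.** The plan gives no target or precision for specificity or PPV, so there is no stated figure to reproduce. Its half-width table covers sensitivity only. For illustration I use the cited 30-patient trial in Section 2.3 (sensitivity 64%, specificity 95%, PPV 88%, NPV 82%). A search of all whole-number tables with n = 30 finds one match: TP 7, FN 4, FP 1, TN 18.

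If the one FP patient is unimaged (exact 95% intervals):
- Specificity: 18/19 = 94.7% (74.0 to 99.9) under the default; 18/18 = 100% (81.5 to 100) under the literal rule.
- PPV: 7/8 = 87.5% (47.3 to 99.7) under the default; 7/7 = 100% (59.0 to 100) under the literal rule.
- Sensitivity 7/11 = 63.6% and NPV 18/22 = 81.8% under both.

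The share of such patients left unimaged is not in the documents. The range, holding TP 7, FN 4 and 19 reference-negative patients, is:

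| PET+, pathology− | Unimaged | Specificity, default | Specificity, literal | PPV, default | PPV, literal |
|---|---|---|---|---|---|
| 1 | 0 | 18/19 = 94.7% | 18/19 = 94.7% | 7/8 = 87.5% | 7/8 = 87.5% |
| 1 | 1 | 18/19 = 94.7% | 18/18 = 100% | 7/8 = 87.5% | 7/7 = 100% |
| 2 | 1 | 17/19 = 89.5% | 17/18 = 94.4% | 7/9 = 77.8% | 7/8 = 87.5% |
| 4 | 2 | 15/19 = 78.9% | 15/17 = 88.2% | 7/11 = 63.6% | 7/9 = 77.8% |
| 4 | 4 | 15/19 = 78.9% | 15/15 = 100% | 7/11 = 63.6% | 7/7 = 100% |

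**5. How many to expect.** Assume 19 reference-negative patients and the two patient-level specificities cited in Section 2.3, 95% and 98.9%.
- Expected PET-positive: 19 × 0.05 = 0.95 and 19 × 0.011 = 0.21.
- At least one: 1 − 0.95^19 = 62.3% and 1 − 0.989^19 = 19.0%.
- Two or more: 24.5% and 1.8%.
- At least one who is also unimaged, if half are unimaged (assumption): 1 − 0.975^19 = 38% and 1 − 0.9945^19 = 10%.

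**6. If the unimaged patient really had a positive node missed at surgery.** The table becomes 8/4/0/18: sensitivity 8/12 = 66.7%, specificity 18/18, PPV 8/8, NPV 18/22. Neither counting the patient as FP nor excluding the patient shows this sensitivity; both give 63.6%. Nor is exclusion an upper bound for PPV. With TP 7, one confirmed FP and one unimaged patient, exclusion gives 7/8 = 87.5%, while a missed node gives 8/9 = 88.9%.

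**The case against.** The best defence is that the imaging condition is deliberate. The 12.2.1.2 default concerns tissue that was removed, and 5.6.2 asks the surgeon only to try to capture the suspicious node. Without imaging, nobody knows whether that node was in the specimen, and calling the patient an FP may charge PET with a surgical miss. This stands as a reason to show more than one analysis. It does not remove the conflict with the cited section.

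Second, the cross-reference to 12.2.1.2 might be read as importing its default, and 13.2.2.1 carries the same cross-reference. That is possible, but the explicit imaging clause in 13.2.3.1 then contradicts what it imports.

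Third, the imaging may exist. Section 5.7.4 expects standard-of-care imaging, 5.7.5 presupposes a follow-up CT or MRI in PET-positive disease, 6.4.4 allows a second PSMA PET in this situation, and 12.2.2 provides a study-paid CT for PET-positive subjects. This stands in part. The rescan and the second PET are optional (5.7.1, 12.2.1.2 i, 6.4.4), and 6.4.2 limits the research CT to lesions outside the pelvis, which conflicts with 12.2.2. A reader might infer that these patients will certainly leave the analysis; the documents do not support that.

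A reader might also infer that the retained node with a negative biopsy is clearly non-evaluable. That is too strong: 13.2.5.1 speaks of insufficient data, this patient has data, and 13.2.1.3 might apply.

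**Conclusion.** The concern holds as a contradiction between a classification rule and the section it cites. Read literally, 13.2.3.1 makes evaluability depend on the PET result. Relative to the plan's own default, any resulting exclusion can only raise specificity and PPV. Relative to the unknown truth, PPV is overstated unless the share of excluded patients with a missed positive node is at least the PPV among classified patients.

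The severity is modest. Zero or one affected patient is likely, given about 19 reference-negative patients and the cited specificities. One patient would move specificity by 5.3 points and PPV by 12.5 points in the illustration, with widely overlapping intervals. Section 13.2 plans no test, so the harm is to the reported estimates and not to a decision rule.

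A reader might infer that sensitivity, which 13.1 names as the main information sought, is also inflated. It is not: TP/(TP+FN) is the same under both rules, and it would be understated if an excluded patient truly had a missed positive node.

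**What to change.** 1. Reword 13.2.3.1 to match 12.2.1.2: PET positive with negative regional pathology is an FP unless post-prostatectomy imaging shows that the PET-positive node was not removed.
2. Classify a retained node with a correctly targeted negative biopsy as FP, as 12.2.1.2 ii implies, and state that this pathology takes precedence over 13.2.1.3.
3. Report the number of non-evaluable patients by PET result.
4. Report all four measures three ways, with unimaged and indeterminate retained-node patients counted as FP (for unimaged patients, the 12.2.1.2 default), excluded, and counted as TP. Only the last shows what a positive node missed at surgery would do to sensitivity and PPV.

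Separately, the follow-up imaging provisions in 5.7.1, 6.4.2 and 12.2.2 must be reconciled.

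Cost: protocol wording and extra tabulations. The analysis change needs no added scans; reconciling the imaging provisions might, depending on how it is done. Specificity and PPV may look slightly less favourable, and some nodes missed at surgery may be counted as FP in the default analysis; the TP variant shows how much that could matter.

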## 5.7. **Post-Prostatectomy Procedures**

- 5.7.1. **PSMA-positive with negative pathology.** Subjects with  $^{68}\text{Ga}$  PSMA-HBED-CC positive nodes without positive nodes on pathology, may be rescanned with CT (or MRI) to determine if the suspicious node was thought to be removed. Additionally, clinicians will have the option to order a 2nd  $^{68}\text{Ga}$  PSMA-HBED-CC PET/CT as described in Section 6.4.4.
- 5.7.2. **PSMA-positive osseous or metastatic lesions.**  $^{68}\text{Ga}$  PSMA-HBED-CC positive osseous or distant metastatic lesions will be followed by other imaging (bone scan, NaF PET, CT or MRI) at the treating physician's discretion and local standard of care.
- 5.7.3. **Biopsy.** Biopsies to determine metastases or provide information for re-staging should be performed at treating physician's discretion and per local

standard of care.

- 5.7.4. **CT or MRI.** Subjects should undergo routine standard of care imaging.
- 5.7.5. Positive disease identified by either Ga PSMA-HBED-CC PET/CT or follow-up conventional imaging will trigger locally performed anatomic measurement of lesion size(s) on both the baseline CT or MRI, and the follow-up CT or MRI of suspected site of disease.

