## 6.4. **Follow-up**

6.4.1. **Pathology.** Results from pathology ordered per standard of care up to 12 months post Ga PSMA-HBED-CC PET/CT, will be obtained for study analysis.

6.4.2. **Follow-up imaging.** Conventional imaging ordered per standard of care up to 12 months post Ga PSMA-HBED-CC PET/CT, will be obtained for study analysis. If the 1st Ga-68 PSMA-HBED-CC PET/CT scan shows lesions outside the pelvic region AND if imaging is NOT obtained per standard of care the research study will obtain a CT (abdomen and pelvis w/ contrast if contrast not contraindicated). Readers will be unblinded to all results and will be specifically informed of the location of the Ga PSMA-HBED-CC PET positive lesions so follow-up measurements may be performed on the same lesions.

6.4.3. **Laboratory.** Results from laboratory reports related to prostate cancer monitoring (e.g. PSA levels) ordered per standard of care up to 12 months post Ga PSMA-HBED-CC PET/CT, will be obtained for study analysis.

6.4.4. **Second Ga PSMA-HBED-CC PET/CT (if medically indicated).** If the 1st Ga PSMA-HBED-CC PET/CT scan shows lymph nodes or visceral (soft tissue) lesions positive for prostate cancer disease, but surgery or biopsy results in negative pathology; the subject may be asked to return to complete a 2nd Ga-68 PSMA-HBED-CC PET/CT imaging visit.

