12.2.1.3. Bone lesions: Given the high rate of false negative biopsies for osseous metastases in subjects with prostate cancer, subjects with negative bone biopsies of  $^{68}\text{Ga}$ -PSMA-HBED-CC PET positive lesions will be further evaluated:

- If pathology demonstrates an alternative diagnoses that is known to be  $^{68}\text{Ga}$ -PSMA-HBED-CC positive (eg Renal Cell Carcinoma metastases, Paget's disease), then this will be considered negative for disease.
- If pathology is indeterminate, then follow-up imaging as described below will be performed as per clinical standards at the site.

12.2.1.4. Although not routinely performed during standard practice, immunohistochemical staining for PSMA of tumor specimens (primary and lymph node metastases) may be performed, although not required.

12.2.1.5. All regions not sampled for biopsy/histopathology will be designated as indeterminate for disease by pathology. Conventional imaging follow-up may be used in these cases to determine tissue status.

12.2.2. Follow-up Imaging will be used as a secondary assessment for prostate cancer in the event pathology information is not available:

All subjects will be tracked for follow-up conventional imaging between 3-12 months post  $^{68}\text{Ga}$ -PSMA-HBED-CC (dedicated CT, MRI and/or bone scan) as per site standard of care. If no follow-up imaging has been performed within the 9 months following the  $^{68}\text{Ga}$ -PSMA-HBED-CC scan, then the research study will pay for an additional follow-up CT scan to be performed in the 9-12

month window post-Ga-PSMA-HBED-CC scan. Follow up imaging will only be performed on subjects that have positive Ga-PSMA-HBED-CC findings because conventional imaging assessment for disease is primarily targeting suspicious lesions identified by Ga-PSMA-HBED-CC PET/CT. Interpretation of follow-up imaging will be performed by local read. Preferably, the follow-up conventional imaging should be the same modality/modalities as the initial staging work-up to allow for reproducible and accurate comparisons. Conventional imaging standards as described below will be used to determine tissue positive for prostate cancer disease. Conventional imaging will not be used to determine negative prostate cancer disease regions due to its inherently low negative predictive value.

Tissue positive for prostate cancer disease based on follow-up imaging:

12.2.2.1. Lymph nodes will be assessed by change in size.

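### The false-positive rule in 13.2.3.1 is stricter than the reference standard it cites, so PET-positive, pathology-negative men without a confirming scan drop out and specificity can only rise or stay the same

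*Combined protocol and SAP*

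**What the plan says.** For a man read as PET-positive for regional nodes, 13.2.3.1 defines a false positive by two further conditions: "pathology at prostatectomy is negative, and imaging after prostatectomy demonstrates that node is no longer present as defined in Section 12.2.1.2". The section it cites sets a different default: "Tissue removed and negative for pathology are considered negative for prostate cancer disease, unless subsequent conventional imaging or" a repeat PSMA PET shows that the targeted tissue was not taken out. Item i of 12.2.1.2 covers a rescan that confirms removal: "If the tissue is confirmed as removed, this is considered negative for disease". Item ii covers tissue still present. A biopsy of the right tissue settles the matter either way; failing that, change in node size is used.

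The neighbouring rules matter too. A true negative (13.2.2.1) needs a negative PET and negative pathology, and no scan. A PET-positive, pathology-negative man can be a true positive (13.2.1.2), but only if imaging shows the node was missed and later evidence shows disease. Anyone who meets none of the four definitions is non-evaluable (13.2.5.1).

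On whether the scan will exist, 5.7.1 says such men "may be rescanned with CT (or MRI) to determine if the suspicious node was thought to be removed"; item i of 12.2.1.2 and 6.4.4 are equally permissive. Section 6.4.2 adds a research CT on another trigger: if the first PET/CT "scan shows lesions outside the pelvic region AND if imaging is NOT obtained per standard of care the research study will obtain a CT". Section 12.2.2 is broader. If nine months pass without imaging, "then the research study will pay for an additional follow-up CT scan to be performed in the 9-12" month window, and "Follow up imaging will only be performed on subjects that have positive" PSMA findings. But it opens by giving follow-up imaging a secondary role, "in the event pathology information is not available", and these men have pathology.

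**The concern.** Specificity and PPV are named in the primary objective (1.1.1). One rule needs a scan to confirm removal; the other needs a scan only to overturn the pathology. For a man with no scan they give different answers, non-evaluable or false positive. The clause in 13.2.3.1 that points to 12.2.1.2 could itself be read as importing the no-scan default, so two analysts could defensibly report different primary results from the same data.

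If the literal reading governs, node-negative men can leave the specificity denominator only when PET called them positive. That is a one-directional selection. Section 13.1 intends the pilot to inform a larger study, possibly together with results from sites using the same reference-standard definitions, so the rule may be carried forward.

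**Working it through.** **The plan's own figure.** The table in 13.1 gives 95% half-widths for sensitivity with 30 patients. With 1.96 × √(p(1−p)/30), sensitivities of 70, 75, 80, 85 and 90% give 16.40, 15.49, 14.31, 12.78 and 10.74%. All five match. The table concerns sensitivity, and the point does not depend on it. Below, sensitivity is TP/(TP+FN); the formula printed in 13.1 has FP in place of FN, which is a separate matter.

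**Rules side by side** for a PET-positive man with negative pathology:

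| Situation | 13.2 read literally | 12.2.1.2 |
|---|---|---|
| Scan shows node gone | False positive | Negative, so false positive |
| No scan | Non-evaluable (13.2.5.1) | Negative by default, so false positive |
| Node still present, targeted biopsy negative | Non-evaluable: node is not gone, disease not shown | Negative (item ii), so false positive |
| Node still present, targeted biopsy positive | True positive (13.2.1.2) | Positive, so true positive |

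**Direction.** Let u be the false positives lost under the literal rule. Reported specificity is TN/(TN+FP−u), which is never below TN/(TN+FP). If v true positives of the 13.2.1.2 kind are also lost for want of a scan, PPV is (TP−v)/(TP−v+FP−u), which can move either way.

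**Illustrative table.** Section 2.3 reports sensitivity 64%, specificity 95%, PPV 88% and NPV 82% for a 30-man study. The only table of 30 that rounds to all four is TP 7, FP 1, TN 18, FN 4 (7/11, 18/19, 7/8, 18/22).

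| Case | Measure | Unscanned man counted as FP | Excluded | Counted as missed TP |
|---|---|---|---|---|
| 1 FP, unscanned | Specificity | 18/19 = 94.7% | 18/18 = 100% | 18/18 = 100% |
| | PPV | 7/8 = 87.5% | 7/7 = 100% | 8/8 = 100% |
| | Sensitivity | 7/11 = 63.6% | 63.6% | 8/12 = 66.7% |
| 2 FP, one unscanned (TN 17) | Specificity | 17/19 = 89.5% | 17/18 = 94.4% | 17/18 = 94.4% |
| | PPV | 7/9 = 77.8% | 7/8 = 87.5% | 8/9 = 88.9% |

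For specificity, excluding the unscanned men is the same as assuming that every one was a surgical miss, so the first two columns bracket it. PPV needs the third column: 88.9% lies outside 77.8% to 87.5%.

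**The other direction.** If the unscanned man is one of the 7 true positives, excluding him gives PPV 6/7 = 85.7% instead of 87.5%, sensitivity 6/10 = 60.0% instead of 63.6%, and unchanged specificity.

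**How often.** The documents give no rate of missing scans, so assume a share u of 10, 25 or 50% among false positives, with 19 node-negative men and specificity s.

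- Chance of losing at least one, 1−(1−(1−s)u)^19: 9.5, 22.2, 39.8% at s = 18/19; 2.1, 5.1, 9.9% at s = 98.9% (the cited 130-man study).
- Long-run reported specificity, s/(s+(1−s)(1−u)): 95.2, 96.0, 97.3% against 94.7%; 99.0, 99.2, 99.4% against 98.9%.

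**The case against.** Requiring the scan is a defensible choice. The default in 12.2.1.2 concerns tissue that was removed, and negative pathology alone does not show that the PET target was in the specimen; 5.6.2 asks only that the surgeon try to capture it. A PET-negative man has no target to miss, so some asymmetry is inherent. This stands as a reason to limit any default to dissected regions and to show the exclusion result alongside. It does not make exclusion neutral, because for specificity exclusion equals the most favourable assumption.

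Missing scans may also be uncommon. Section 5.7.4 expects routine imaging and 12.2.2 offers a study-paid CT to PET-positive subjects. This stands too: the number affected could be zero. But no provision clearly requires the scan for a man with pelvic-only findings and negative pathology.

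The effect is small beside sampling error. Exact 95% intervals are 74.0 to 99.9% for 18/19 and 81.5 to 100% for 18/18, and sections 13.1 and 13.2 describe a sensitivity-focused pilot with descriptive statistics only. That bears on severity; it does not remove the mismatch.

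**Conclusion.** The point holds at low severity. Read literally, 13.2.3.1 with 13.2.5.1 drops men whom 12.2.1.2 would make reference-negative, and this can only raise specificity or leave it alone. The size rests on assumed scan rates: at those assumed above, the long-run shift is about 0.1 to 2.6 percentage points (99.0 against 98.9; 97.3 against 94.7), though a single man moves the illustrative table by 5.3 points (100 less 94.7).

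Stronger readings are tempting but not supported:

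- A reader might infer that the plan leaves the unscanned man unclassified. It does not: 13.2.5.1 makes him non-evaluable.
- A reader might infer that the two sections agree whenever a scan exists. They do not when the node persists and a targeted biopsy is negative.
- A reader might infer that PPV is always inflated. It can fall, because true positives under 13.2.1.2 need the same scan.
- A reader might infer that sensitivity is distorted by losing a false positive. With TP/(TP+FN) it is not.

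**What to change.** 1. Amend 13.2.3.1 so that a man who is PET-positive in a dissected region with negative pathology is a false positive unless follow-up imaging or biopsy shows the target was not resected. In that case item ii of 12.2.1.2 decides, and a negative, correctly targeted biopsy makes him a false positive. Define dissected regions by the labels used under 5.6.3.
2. Report how many of these men had a confirming scan, and give specificity and PPV three ways: unscanned men counted as false positives, excluded, and counted as missed true positives. The first two bracket specificity; the first and third bound PPV.

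The cost is a wording amendment and a few extra figures. No extra CT is proposed: because of how 12.2.2 opens, extending it to men with pathology could add procedures.

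The downside is that an unresected true node with no scan would count as a false positive in the main analysis. In the illustration, one such man gives TP 6, FP 2, TN 18, FN 4: sensitivity 6/10 = 60.0%, specificity 18/20 = 90.0%, PPV 6/8 = 75.0%, against true values of 63.6, 94.7 and 87.5%. Left/right-only labels make such a miss harder to rule out, and reported specificity may look less favourable. Unscanned men who are PET-positive only outside the dissected regions would remain non-evaluable and should be counted separately.
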